### Continued Access to Study Intervention after the End of the Study

The study will remain open until all participants have discontinued study intervention and completed their last expected visit/contact.

After the participant's last visit, AstraZeneca will continue to supply selumetinib to participants whilst they are still receiving clinical benefit or until meeting any other discontinuation criteria.

AstraZeneca will continue to supply selumetinib in the continued access phase of this study while, in the opinion of the Investigator, the participant is benefiting.

In the event that product development reaches a point where alternative product supply options become available, then these alternative product supply options will be discussed by AstraZeneca with the Investigator. AstraZeneca will work with the Investigator to transition the participant(s) to alternative supply, where possible.

In the event that a roll-over or safety extension study is available at the time of the final data cut-off (DCO) and database closure, participant(s) currently receiving treatment with selumetinib may then be transitioned to such a study, and the current study may reach its end. The roll-over or extension study would ensure treatment continuation with visit assessments per its protocol, as applicable. Any participant who would be eligible to move to such a study would be given a new informed consent, as applicable.

**Disclosure Statement:** This is a single group treatment study with one arm that has no masking.

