a. After 25 cycles (or discontinuation of selumetinib) participants who are aged < 5 years will enter a long term safety follow-up and assessments will be performed as per Table 3. After 25 cycles of treatment if participants are > 5 years of age and unable to access commercial supply and are still receiving clinical benefit participants may be able to remain on treatment in the study. Assessments will revert to standard of care at the particular site. There will be no more data collection except SAE, overdose and pregnancy reporting. All SAEs, overdoses and pregnancies will be reported until 30 days after last dose.

b. Once participants attain a BSA between 1.10 and 1.29 m^2 they will be encouraged to completely transition to the capsule formulation, if feasible, although all participants must remain on the granule formulation until after they have completed their third cycle of treatment.

c. An EoT visit will be performed for participants who permanently discontinue study intervention for any reason (except for death, lost to follow-up, or withdrawal of consent). The EoT visit should be performed as soon as possible after the end of treatment.

d. Calculation of BSA should be done at the specified time points but since BSA determines the dose of selumetinib it should also be calculated more frequently, as appropriate, depending on the age and growth rate of the child.

e. Assessment of baseline disease characteristics includes documenting location of the target and non-target PN (if applicable), any PN-related symptoms and results of any previous genetic testing for NF1. (Participants recruited under CSP Version 1.0 will have this data entered in the EDC if available retrospectively.)

- f If clinical safety laboratory assessments, urinalysis and performance status have been done within 14 days of starting study intervention they do not need to be repeated on C1D1 if the participant's condition has not changed. If laboratory procedures were performed for alternate reasons prior to signing consent (but within the 28 day screening window), these can be used for screening purposes with consent of the legally authorised representative (parent or guardian) of the participant.

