#### **Dose-finding Process**

Data from three evaluable participants in Cohort 1 (participants aged  $\geq 4$  to < 7 years of age) are needed for the dose-finding phase. After the completion of at least one cycle of dosing in the first 3 evaluable participants, the SRC will evaluate the PK, safety, and tolerability of the granule formulation. To ensure that there are 3 evaluable participants in each dose finding phase, a maximum of 4 participants will be dosed. Should participants be classed as non-evaluable for the dose finding phase, additional participants will be dosed to ensure there is a minimum of 3 evaluable participants (maximum 4 evaluable participants). Dosing of additional participants in the study will be paused whilst the SRC convenes to assess the PK and safety data at the end of the dose-finding phase in the first 3 evaluable participants.

If the SRC determines that the selumetinib AUC0-12 and safety are within the acceptable criteria (See Section 6.1.2.1) dosing of additional participants into Cohort 1 will continue, and dosing in the dose finding phase for Cohort 2 (participants aged  $\geq 1$  to < 4 years) will commence (as described below).

If the SRC determines that the selumetinib AUC0-12 and safety are not within the acceptable criteria (See Section 6.1.2.1) dose adjustments will be made. Additional participants will be dosed into Cohort 1 in order to have an additional 3 evaluable participants. The dose-finding phase will continue to be assessed in this way until the granule formulation dose schema is identified and recommended for Cohort 1 (see Figure 2).

Once the selumetinib granule formulation dose schema is identified for Cohort 1, dosing in cohort 2 will commence in order to have 3 evaluable participants in Cohort 2 in the dose-finding phase. After the completion of at least one cycle of dosing in the first 3 evaluable participants, the SRC will evaluate the PK, safety, and tolerability of the granule formulation at this dose schema. To ensure that there are 3 evaluable participants in each dose finding phase, a maximum of 4 participants will be dosed. Should participants be classed as non-evaluable for the dose finding phase, additional participants will be dosed to ensure there is a minimum of 3 evaluable participants (maximum 4 evaluable participants). Dosing of additional participants in Cohort 2 will be paused whilst the SRC convenes to assess the PK and safety data in the first 3 evaluable participants.

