3.1 Timing of Analyses

There are 3 planned DCOs for this study.

1 Pharmacokinetic, dose-finding, and primary safety analysis (DCO1): DCO1 will occur after all participants have had the opportunity to complete 3 cycles of treatment. This primary analysis will confirm the recommended granule formulation dose schema and assess the PK, safety/tolerability, and palatability. The timing of DCO1 may be different for the Global Cohorts (Cohorts 1 and 2) from the Japan Cohort based on their date of Last Subject In.

2 Safety and efficacy of the granule formulation (DCO2):

DCO2 will occur after all participants in the study (Global and Japan Cohorts) have had the opportunity to complete 25 cycles (or terminated selumetinib); this analysis will provide additional PK and safety/tolerability data, as well as palatability and efficacy data.

3 Long term safety follow-up for participants until they reach the age of 5 years or commence an alternative systemic NF1-PN treatment, whichever is the earlier (Final analysis and DCO3):

DCO3 and final analysis will occur when all participants in the study (Global and Japan Cohorts) have had the opportunity to complete their last assessment in the study, including the safety follow-up for participants aged < 5 years. All of the safety/tolerability analyses will be updated with the data captured after DCO2 (safety of the granule formulation).

The different analyses planned for the DCOs are provided in [Table 1](#).

Table 1 Summary of Outcome Variables and Timing of Analyses

Outcome variable	Timing of analyses
Study population/demographic data	
Outcome variable	Timing of analyses
Disposition	DCO1, DCO2, and DCO3

Analysis sets	DCO1
Demographic characteristics	DCO1
Baseline and disease characteristics	DCO1
Important protocol deviations	DCO1, DCO2, and DCO3
Medical history	DCO1
Prior and concomitant medication	DCO1, DCO2, and DCO3
Efficacy data	
ORR CCI	DCO2
Clinical outcome assessment data	
Parent-reported palatability	DCO1 and DCO2
CCI	DCO2
CCI	DCO2
CCI	DCO2
CCI	DCO2
Outcome Variable	Timing of analyses
CCI	DCO2
CCI	DCO2
Safety Data	
Exposure and treatment compliance	DCO1, DCO2, and DCO3
Adverse events	DCO1, DCO2, and DCO3
Laboratory measurements	DCO1, DCO2, and DCO3
Vital signs (including height, weight, and BSA)	DCO1, DCO2, and DCO3
ECG and ECHO	DCO1, DCO2, and DCO3
Ophthalmologic assessments	DCO1, DCO2, and DCO3
Knee (or wrist) MRI/X-ray	DCO1, DCO2, and DCO3
Performance status	DCO1, DCO2, and DCO3

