3.3.1 Baseline and Change from Baseline Definition

Baseline is defined as the last non-missing value obtained prior to the first dose of selumetinib.

Assessments on the day of the first dose where time is not captured will be considered prior to the first dose if such procedures are required by the CSP to be conducted before the first dose.

If two or more measures are recorded on the same day with no time (or on the same day with the same time/timepoint), then the average will be used as the baseline. For nonnumeric laboratory tests (ie, some of the urinalysis parameters) where taking an average is not possible, then the best value would be taken as baseline as this is the most conservative.

In all summaries, the change from baseline variables will be calculated as the posttreatment value -minus the value at baseline.

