4 STATISTICAL ANALYSIS

This section provides information on the definitions, derivations, and analysis/data presentation per domain.

Not all analyses will be performed for each DCO. [Table 1](#) provides detailed information on the expected outputs.

For DCO1 and DCO2, all available data will be used for the planned analyses as specified in [Table 1](#). For DCO3, the data of a subset of participants who are aged < 5 years after 25 cycles of selumetinib treatment or discontinuation of study intervention will be presented.

The starting dose schema was approved by the SRC as the recommended dose schema in both cohorts at the end of the dose-finding phase.

The analysis will be presented for the Global Cohorts (Global Cohort 1, Global Cohort 2, and both Global Cohorts combined), the Japan Cohort, and for all participants (all cohorts combined), except for the PK analyses where the Global Cohorts and the Japan Cohort will be presented separately without combining.

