4.6.6.2 Presentation

All vital signs (temperature, systolic and diastolic blood pressure, pulse rate, respiratory rate, and oxygen saturation) and growth parameters (height, weight, and BSA) will be summarised using descriptive statistics over time in terms of absolute values and change from baseline by scheduled visit.

Vital sign data will be presented graphically using boxplots for absolute values and changes from baseline by scheduled visit.

Individual BSA will be plotted against the study day. Historical measurements of weight and height will be presented on the x-axis as negative study days. Off-treatment data for participants who entered the long-term safety follow-up (participants < 5 years of age after 25 cycles of treatment or when they terminate treatment with selumetinib) will be included in the figure but presented with different symbols.

All vital sign, including BSA group, data will be listed.

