4.6.8.2 Presentations

A summary table of absolute values and change from baseline of LVEF, end diastolic, and end systolic left ventricular volumes will be presented for each scheduled visit.

For ejection fraction decrease, a shift table showing CTCAE grades from baseline to maximum on-treatment will be produced.

All ECHO data will be listed.

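### Left ventricular volumes are summarised only as raw values and raw change in growing children with no control arm, so at later visits (mainly Cycle 9 onward) normal growth is mixed into the volume change.

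*SAP*

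**What the plan says.** Protocol 8.3.5 requires LVEF and both left ventricular volumes to be recorded at every ECHO. SAP 4.6.8.2 then plans "A summary table of absolute values and change from baseline of LVEF, end diastolic, and end systolic left ventricular volumes" for each scheduled visit. It adds a CTCAE shift table for ejection fraction decrease only, and a listing of all ECHO data. Under SAP 3.3.1, "the change from baseline variables will be calculated as the posttreatment value" less the baseline value, with no adjustment for age or size.

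The Synopsis disclosure statement says "This is a single group treatment study with one arm that has no masking". Growth during the study is expected: footnote d to Protocol Table 2 says of BSA that "it should also be calculated more frequently, as appropriate, depending on the age and growth rate of the child". SAP 4.6.6.2 states that "growth parameters (height, weight, and BSA) will be summarised using descriptive statistics over time", separately from the ECHO table. BSA normalisation is planned only for PK parameters (SAP 4.4.1), where it uses the child's BSA on the corresponding PK visit.

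On timing, SAP 3.1 states that "DCO1 will occur after all participants have had the opportunity to complete 3 cycles of treatment", and SAP section 4 adds "For DCO1 and DCO2, all available data will be used for the planned analyses". ECHO data are reported at all three data cut-offs (SAP Table 1).

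**The concern.** In a young child, left ventricular volume rises as the body grows. A raw change from baseline adds that growth to any effect of the drug, and with one arm no comparison group shows how much of the rise is growth. The mean volume change can therefore climb over visits with no drug effect. A true change can also be taken for growth.

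ECHO is one of the assessments in the primary safety endpoint, and Protocol Table 4 says routine ECHO matters especially in very young patients, whose symptoms are harder to detect. Two rows of that output would be hard to interpret at the later visits, where the effect is largest. What is at stake is how these two descriptive rows are read. No decision rule in either document uses the volumes.

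**Working it through.** The plan gives no figure for the ECHO volumes, so there is nothing to reproduce. The check has four steps.

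**1. Follow-up (Protocol Table 2, 28-day cycles).** Cycle 25 Day 1 is 24 × 28 = 672 days after first dose, about 22 months. Cycle 9 Day 1 is 8 × 28 = 224 days, 1/3 of that span. Cycle 5 Day 1 is 4 × 28 = 112 days, 1/6. Cycle 2 Day 1 is 28 days, 1/24.

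**2. Volume change from growth alone.** Two inputs are assumptions, because the documents give neither: BSA growth *g* of 10% to 30% over 672 days at a steady proportional rate, and volume rising as BSA to the power *b*, with *b* from 1.0 to 1.4. At a fraction *f* of the span, raw volume is multiplied by (1+g)^(b·f). Volume divided by same-day BSA is multiplied by (1+g)^((b−1)·f).

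| Visit | Raw, lowest (g = 10%, b = 1.0) | Raw, highest (g = 30%, b = 1.4) | Indexed, b = 1.0 | Indexed, b = 1.4 |
|---|---|---|---|---|
| Cycle 2 | 1.10^(1/24) = 1.004 | 1.30^(1.4/24) = 1.015 | 1.000 | 1.002 to 1.004 |
| Cycle 5 | 1.10^(1/6) = 1.016 | 1.30^(1.4/6) = 1.063 | 1.000 | 1.006 to 1.018 |
| Cycle 9 | 1.10^(1/3) = 1.032 | 1.30^(1.4/3) = 1.130 | 1.000 | 1.013 to 1.036 |
| Cycle 25 | 1.10 | 1.30^1.4 = 1.444 | 1.000 | 1.039 to 1.111 |

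With no drug effect, raw volume rises by up to about 1.5% at Cycle 2, 2% to 6% at Cycle 5, 3% to 13% at Cycle 9 and 10% to 44% at Cycle 25. Indexing removes all of this at *b* = 1.0. At *b* = 1.4 it leaves about 4% to 11% at Cycle 25.

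**3. LVEF.** LVEF = (EDV − ESV)/EDV, where EDV and ESV are the end-diastolic and end-systolic volumes, so a common growth factor cancels. With illustrative volumes of 30 and 10.5 mL, 20% growth gives 36 and 12.6 mL. EDV rises by 6 mL, LVEF stays at 65.0%, and EDV/BSA is unchanged if *b* = 1.

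**4. What DCO1 contains.** Under the dose-finding process in Protocol 6.1.2, "Once the selumetinib granule formulation dose schema is identified for Cohort 1, dosing in cohort 2 will commence", and further Cohort 2 dosing waits for one cycle in its first three evaluable children. With no review time and no dose change, the first Cohort 1 children have at least 28 + 28 + 84 = 140 days from first dose at DCO1. The Cycle 5 ECHO is due by day 112 + 7 = 119, so they have Cycle 2 and Cycle 5 ECHOs if still on treatment. A child dosed last may have only the Cycle 2 ECHO, since Table 2 schedules none at Cycles 3 or 4. At these visits the growth effect is at most about 6%. The 140 days is a minimum: slower accrual would bring some later visits into DCO1.

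**The case against.** The case for leaving the table alone has real weight.

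- **LVEF carries the cardiac decisions.** The cardiac risk named in Protocol Table 4 is LVEF decrease. LVEF drives eligibility, troponin testing, the follow-up ECHO trigger and the shift table. The cardiac terms of special interest are ejection fraction, oedema and ventricular dysfunction. This stands, and it limits the point to two descriptive rows.
- **The planned outputs already show growth.** LVEF appears beside the volumes in the same table. BSA is summarised by visit and plotted for each child, and results are split into the 4 to under 7 and the 1 to under 4 age cohorts. A reader can divide a cohort's mean volume by its mean BSA at each visit. That stands as an approximate adjustment. A ratio of two means is not the mean of the children's own indices, it gives no spread, and nothing pre-specifies it.
- **Height, weight and BSA are also shown as raw change.** True, but those rows are meant to show growth. The volume rows are there for cardiac safety.
- **The size is assumed.** This stands. The 44% combines both upper bounds and is not an expected value.
- **Indexing is imperfect.** This also stands. Some growth effect remains if volume rises more steeply than BSA. A rule tied to same-visit BSA would also leave out the unscheduled ECHOs that Protocol 8.3.5 calls for when cardiac deterioration is suspected, and that SAP 3.3.4 and 3.3.5 assign to visit windows. The fix has to cover these.

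A reader might infer that the raw rows will produce a false signal of drug-related dilatation, or that cardiac safety monitoring is compromised. The documents support neither. They do not list dilatation as a risk, a term of special interest or a threshold, and the measure that triggers action is free of this growth effect.

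**Conclusion.** The point holds as a cheap improvement to a safety table. At later visits, mainly Cycle 9 onward and so at DCO2 and DCO3, the raw volume change mixes normal growth with any drug effect, and no planned summary separates them. The direction follows from growth. The size, about 10% to 44% at Cycle 25, rests wholly on the assumed BSA growth and exponent, and on sites recording unindexed volumes, which the documents do not state either way. Growth during long-term follow-up to age 5 would add to it and is not in that range.

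A reader might infer that the problem is equally serious at every data cut-off. It is not: at the visits DCO1 is certain to include, it is about 6% or less on these assumptions. Sample size, the primary PK analysis and LVEF are not affected.

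**What to change.** In SAP 4.6.8.1 define end-diastolic and end-systolic volume index (mL/m²). In SAP 4.6.8.2 keep the raw rows and add both indices, with value and change from baseline.

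Use one BSA rule for every ECHO, whether scheduled, unscheduled or in long-term follow-up: take the BSA closest in date to the actual ECHO date, or calculate it from height and weight by the formula in Protocol 8.3.2. List the gap in days. Footnote that some growth effect may remain after indexing.

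No new measurements are needed. Of the 10 ECHO time points in Protocol Table 2, BSA is scheduled at 8 (screening and Cycles 2, 5, 9, 13, 17, 21 and 25). Height and weight are scheduled at the other two (end of treatment and 30-day follow-up).

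The cost is SAP wording, two derived variables and the matching rule. The match will be imperfect at some unscheduled and long-term ECHOs. In Table 3, on-treatment ECHOs come about every 3 cycles but BSA every 6, so about half would use a BSA some 84 days away. That is 84/672 = 1/8 of the span, and it shifts the index by about 1.10^(1/8) = 1.012 to 1.30^(1/8) = 1.033, or 1% to 3%.

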4.6.9 Ophthalmologic Examinations

4.6.9.1 Definitions and Derivations

An ophthalmologic examination (best corrected visual acuity, intraocular pressure, and slit-lamp fundoscopy) will be evaluated at the times outlined in the CSP and as clinically indicated whilst the participant is on study intervention.

The rules described in Sections 3.3.1, 3.3.5, and 3.3.6 of this document considering definition of baseline, visit windows, and how to handle multiple records are followed.

4.6.9.2 Presentations

A frequency table showing the number of participants with their ophthalmologic examination results (Fundoscopy performed: Yes, No; Type of fundoscopy performed: Indirect, Slit lamp; Indirect and Slit lamp result: normal, abnormal, clinically not significant; or abnormal, clinically significant) by eye (left/right) for each scheduled visit will be presented.

Intraocular pressure will be presented graphically using box plots for absolute values and changes from baseline for each scheduled visit – one box plot for each eye.

Ophthalmology examination data will also be listed for participants, including a description of the abnormalities and relevant baseline result.

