## Type of Participant and Disease Characteristics

- 2 All participants must have a diagnosis of NF1 with symptomatic inoperable PN where:
  - (a) Participants must have PN and at least one other diagnostic criterion for NF1 (Legius 2021)
    - Six or more café-au-lait macules (> 5 mm in greatest diameter in prepubertal participants and > 15 mm in greatest diameter in post pubertal participants)
    - Freckling in the axillary or inguinal region
    - Optic pathway glioma
    - Two or more iris Lisch nodules identified by slit lamp examination or two or more choroidal abnormalities defined as bright, patchy nodules imaged by optical coherence tomography/near-infrared reflectance imaging
    - A distinctive osseous lesion such as: Sphenoid wing dysplasia, anterolateral bowing of the tibia or pseudoarthrosis of a long bone (Note: Sphenoid wing dysplasia is not a separate criterion in case of an ipsilateral orbital plexiform neurofibroma)
    - A heterozygous pathogenic NF1 variant with a variant allele fraction of 50% in apparently normal tissue such as white blood cells
    - A parent with NF1 who meets the diagnostic criteria above
  - (b) A PN is defined as a neurofibroma that has grown along the length of a nerve and may involve multiple fascicles and branches. A spinal PN involves two or more levels with

connection between the levels or extending laterally along the nerve. A histologic confirmation of the PN is not necessary in the presence of consistent clinical and radiographic findings, but should be considered if malignant transformation of a PN is clinically suspected.

- (c) Inoperable is defined as a PN that cannot be completely surgically removed without a risk of substantial morbidity due to encasement of, or close proximity to, vital structures, invasiveness, or high vascularity of the PN; or unacceptable risk from the general anaesthetic as assessed by the Investigator
- (d) Symptomatic is defined as clinically significant symptoms or complications caused by the PN, as judged by the investigator; symptoms may include, but are not limited to, pain, motor dysfunction and disfigurement (examples of complications include PN displacing trachea, or PN causing bladder obstruction and hydronephrosis).

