  - Intraocular pressure > 21 mmHg (or ULN adjusted by age) or uncontrolled glaucoma (irrespective of IOP). Participants with known glaucoma that is clinically pain-free, has no clinically meaningful vision (light perception only or no light perception) and has increased IOP may be permitted.
  - Participants with any other significant abnormality on ophthalmic examination should be reviewed for potential eligibility.

- Ophthalmological findings secondary to long-standing optic pathway glioma (such as visual loss, optic nerve pallor or strabismus) or longstanding orbito-temporal PN (such as visual loss, strabismus) will NOT be considered a significant abnormality for the purposes of the study.
- 10 Have any unresolved chronic toxicity with CTCAE Grade  $\geq 2$  which are associated with previous therapy for NF1-PN (except hair changes such as alopecia or hair lightening)
- 11 Participants who have previously been treated with a MEKi (including selumetinib) and have had disease progression, or due to toxicity have either discontinued treatment and/or required a dose reduction.
- 12 Have had major surgery within 4 weeks of the first dose of study intervention, with the exception of surgical placement for vascular access. Have planned major surgery during the treatment period.
- 13 Have inadequate haematological function defined as:
  - An absolute neutrophil count  $< 1500/\mu L$
  - Haemoglobin < 9g/dL
  - Platelets <  $100,000/\mu$ L
  - Have had a transfusion (of red cells or other blood derived products) within the 28 days prior to study entry (date of ICF signature).

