4.6.10.2 Presentations

A frequency table showing the number of participants with their diagnosis of the Knee/Wrist MRI/X-ray (normal, abnormal, clinically not significant; or abnormal, clinically significant) for each scheduled visit will be presented.

All Knee/Wrist MRI data will be listed, including a description of the abnormalities.

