4.6.11.2 Presentations

Shift tables showing score changes from baseline to worst score on treatment will be produced. The performance status score will be listed along with a text description of the score as described in Appendix H of the CSP.

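### The planned eye and growth-plate tables do not give the number of children with a new or worsened finding, and visual acuity has no summary at all

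*SAP*

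**What the plan says.** Protocol Section 3 makes the ophthalmologic assessment and knee/wrist imaging components of the primary safety endpoint. SAP 4.6.9.1 defines the eye examination: "An ophthalmologic examination (best corrected visual acuity, intraocular pressure, and slit-lamp fundoscopy) will be evaluated" at the protocol times.

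SAP 4.6.9.2 then plans three outputs:
- A table: "A frequency table showing the number of participants with their ophthalmologic examination results", by eye and scheduled visit, in the three result classes.
- A figure: "Intraocular pressure will be presented graphically using box plots for absolute values and changes from baseline for each scheduled visit", one plot per eye.
- A listing, "including a description of the abnormalities and relevant baseline result".

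No table or figure is named for visual acuity.

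For growth plates, SAP 4.6.10.2 plans "A frequency table showing the number of participants with their diagnosis of the Knee/Wrist MRI/X-ray" per scheduled visit in the same three classes. Its listing sentence names MRI but not X-ray, and does not mention the baseline result.

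For performance status, by contrast, SAP 4.6.11.2 states: "Shift tables showing score changes from baseline to worst score on treatment will be produced".

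On entry, protocol 5.2 criterion 9 addresses "Ophthalmological findings secondary to long-standing optic pathway glioma (such as visual loss, optic nerve pallor or strabismus", together with similar findings from long-standing orbito-temporal PN. These do not count as significant abnormalities. Any other significant eye abnormality is reviewed for eligibility and not excluded outright.

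**The concern.** A per-visit count of abnormal results is a prevalence. The safety question is incidence: how many children developed a finding, or got worse, on selumetinib. The two agree only if every child starts normal and findings persist once they appear. For eyes, the protocol expects some children not to start normal.

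The adverse event route does not fully replace the missing summary. Protocol 8.4.5 says eye examination results will be summarised in the study report. It then draws the consequence that deterioration is an adverse event only if it is serious, leads to discontinuation or is judged clinically relevant. Protocol 8.4.13 applies the same rule to adverse events of special interest found by examination. For visual acuity, the restriction on reporting is therefore in force while the summary that justifies it is not planned. Protocol Table 4 adds that young children may have difficulty communicating visual disturbance, so measured change matters more here than in older patients.

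**Working it through.** The plan states no figure on this point, so there is nothing to reproduce. The check asks what the planned tables can and cannot identify. Sample sizes are redacted and no baseline abnormality rate is given, so n and b below are assumptions shown over a range.

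**1. New cases at one visit.** Let n children be examined at both times, b abnormal at baseline and v abnormal at the visit. The two per-visit counts fix the number newly abnormal only within

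max(0, v − b) to min(v, n − b).

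| n | b | v | Newly abnormal | As % of those normal at baseline (n − b) |
|---|---|---|---|---|
| 10 | 2 | 2 | 0 to 2 | 0% to 25% of 8 |
| 20 | 4 | 4 | 0 to 4 | 0% to 25% of 16 |
| 20 | 6 | 6 | 0 to 6 | 0% to 42.9% of 14 |
| 30 | 6 | 6 | 0 to 6 | 0% to 25% of 24 |
| 30 | 0 | 2 | exactly 2 | 6.7% of 30 |

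The last row shows that the ambiguity at a single visit disappears when nobody is abnormal at baseline. Missed visits widen the ranges. A move from abnormal not clinically significant to clinically significant is hidden in the same way.

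**2. Cases over the whole treatment period.** Protocol Table 2 schedules five on-treatment eye examinations (Cycles 2, 5, 9, 13 and 21) and two growth-plate images (Cycles 13 and 25). With no abnormal baselines and one abnormal result at each visit, the eye table fits 1 to 5 children and the growth-plate table fits 1 to 2. Even with clean baselines, per-visit counts do not give the number ever affected.

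**3. Unscheduled examinations.** Protocol 8.3.6 requires a complete examination when visual symptoms occur, which may fall between visits. SAP 3.3.4 keeps only the value closest to the scheduled date in each window, and SAP 3.3.5 gives unscheduled visits no row of their own. Cycle 2 Day 1 is Day 29 and Cycle 5 Day 1 is Day 1 + 4 × 28 = 113. The midpoint is (29 + 113)/2 = 71, and the rule subtracts one day, so the Cycle 2 eye window runs from Day 2 to Day 70. Suppose an examination is normal on Day 29 and a symptom-triggered one is abnormal on Day 50. The table shows normal. Participant-level extremes under 3.3.4 and 3.3.5 use all post-baseline values, so a baseline-to-worst shift would show the abnormal result.

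**4. Growth plates at baseline.** The protocol's NF1 criteria include "anterolateral bowing of the tibia or pseudoarthrosis of a long bone", and no exclusion criterion mentions growth plates. That makes an abnormal baseline image possible. No text says that such lesions make the physeal reading abnormal.

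**The case against.** The strongest reply is that other outputs already carry the information. Intraocular pressure is shown as change from baseline. The eye listing puts the baseline result beside each abnormality, and in a small trial it can be read child by child. SAP 4.6.2.2 tabulates ocular toxicity and physeal dysplasia as adverse events of special interest, so clinically relevant events reach a table. Criterion 9 excludes current or past RPED/CSR and RVO, so the best-known retinal toxicities should start at zero. Of the tolerated eye findings named, only optic nerve pallor is clearly a fundoscopy result. All of this stands, and it narrows the point. It leaves no summary of acuity and no count of sub-threshold deterioration.

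A second reply is that the SAP is consistent. Graded or scored measures get shifts, while investigator readings such as ECG interpretation get visit frequencies. Urinalysis is listed only, and protocol 9.4.3.1 makes further shifts optional. It is true that not all laboratory data get shifts. But SAP 4.6.3.2 gives ungraded blood parameters a count of on-treatment increases or decreases, with a baseline-based denominator. That is the kind of count missing here.

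A third reply is that acuity tests differ by age, so pooling scores would mislead. That argues for change categories within each child. It does not argue for having no summary.

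A reader might infer that pooling MRI with X-ray, or knee with wrist, spoils the imaging table. Protocol 8.3.7 holds the modality constant within a child, and the joint too except where imaging it is not possible. A within-child shift would therefore mostly compare like with like.

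**Conclusion.** The point holds as a should-fix matter of presentation for a primary safety component. The fundoscopy and knee/wrist tables do not give the number of children with a new or worsened finding, and visual acuity has no summary. Under the assumed inputs (10 to 30 children, 20% to 30% abnormal at baseline, an unchanged count at the visit), the undetermined share runs from 0% up to 25% or 42.9% of those normal at baseline. The true size depends on redacted sample sizes and unstated baseline rates.

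The eye part rests on explicit entry text. The growth-plate part is weaker: it rests on the cumulative-count argument in step 2 and on a possible, undocumented, abnormal baseline.

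A reader might go further and infer that new eye or growth-plate toxicity cannot be detected from the study's outputs. The documents do not support that, because the adverse event tables, the eye listing and the intraocular pressure plots remain. Nor would a shift table separate drug effect from NF1 in a single-arm study. It would only give the count that such a judgement needs.

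**What to change.** In SAP 4.6.9.2, add:
- A shift table from baseline to worst on-treatment fundoscopy result, by eye, using all post-baseline values including unscheduled ones. Report the number new or worsened among participants with a baseline and an on-treatment result.
- A within-child, by-eye summary of change in best corrected visual acuity, using improved / stable / worsened where test scales differ.

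In SAP 4.6.10.2, add the same baseline-to-worst shift for the knee/wrist result. State that the listing covers X-ray as well as MRI and carries the baseline result.

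Keep the per-visit tables. While editing, correct SAP 4.6.9.1, which cites Sections 3.3.1, 3.3.5 and 3.3.6 for baseline, visit windows and multiple records. The window rules are in 3.3.4, and 3.3.6 concerns missing data.

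The cost is three or four tables from data already collected. The main work is to put acuity on a common scale, or to define the change categories, before database lock.
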